#### 10.1.4 Statistical analysis plan

The binomial proportion and its 90% one-sided exact confidence interval will be

used to estimate the overall response rate, the complete response rate, and the proportion of participants who experience a Grade 3 or higher toxicity. If the lower bound of the 90% exact confidence interval for the overall response rate is  $> 0.10$ , then the null hypothesis will be rejected.

Changes in CD4 counts and HIV viral load will be evaluated using generalized estimating equations.

To assess the effect of pomalidomide treatment on serum cytokine levels, general estimating equations (GEE) will be used to evaluate changes in cytokine levels from baseline. Logistic regression analyses will be used to determine if changes in cytokine levels from baseline are associated with clinical response.

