## **1.0 OBJECTIVES**

### **1.1 Hypotheses**

- 1.1.1 Pomalidomide will induce an overall response rate of at least 30% in HIV-positive individuals with Kaposi sarcoma in sub-Saharan Africa.
- 1.1.2 Pomalidomide will be safe and well tolerated at the dose(s) tested in individuals with Kaposi sarcoma in sub-Saharan Africa.
- 1.1.3 Pomalidomide will not adversely affect CD4 counts and HIV control in HIV-positive individuals with Kaposi sarcoma in sub-Saharan Africa.

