- Total bilirubin:  $\leq 1.5$  times the upper limit of normal (ULN), unless the participant is receiving an antiretroviral drug known to be associated with increased bilirubin, in which case the direct fraction should be  $\leq 2$  times the ULN.
- Serum AST (SGOT) / ALT (SGPT):  $\leq 2.5 \times \text{ULN}$
- Estimated or measured creatinine clearance  $\geq 60 \text{ mL/minute}$  ( $1.00 \text{ mL/s}$ ) (serum creatinine  $\leq 2.0 \text{ mg/dL}$  /  $176.8 \mu\text{mol/L}$ )

3.1.8 Currently receiving local standard of care ART for  $\geq 12$  weeks, with HIV viral load  $\leq 400$  copies/mL within the preceding 12 weeks prior to enrollment.

Participants are required to be on antiretroviral regimens that are in accordance with the current International AIDS Society guidelines concurrently with chemotherapy. Excepting agents containing zidovudine, which is prohibited, the specific agents are at the discretion of the Investigator and the use of investigational ART agents currently available on an expanded access basis is allowed.

3.1.9 A FCBP is a female who has achieved menarche at some point, is  $< 60$  years of age, and who meets one of the following criteria:

- 1) has not undergone a hysterectomy or bilateral oophorectomy, or
- 2) has not been naturally postmenopausal (amenorrhea following cancer therapy does not rule out childbearing potential) for at least 24 consecutive months (i.e., has had menses at any time in the preceding 24 consecutive months), or
- 3) does not have a serum or plasma FSH  $>40 \text{ mIU/mL}$  and a history of amenorrhea  $\geq 1$  year

FCBP must have a negative serum or urine pregnancy test with a sensitivity of at least  $25 \text{ mIU/mL}$  within 14 days prior to enrollment and again within 24 hours of starting pomalidomide and must either commit to continued abstinence from heterosexual intercourse or, if complete abstinence cannot be assured, they must begin TWO acceptable methods of birth control, including one of the following highly effective, long-acting methods, DepoProvera, an intrauterine device (IUD), an implant\*, or bilateral tubal ligation, if it can be verified that the procedure was performed, and one additional effective method AT THE SAME TIME, at least 28 days before she starts taking pomalidomide. FCBP must also agree to ongoing pregnancy testing.

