### **3.3 Number of Participants to be Enrolled**

- 3.3.1 Proposed sample size

This study will enroll 26 participants.

- 3.3.2 Accrual rate

Approximately two participants per month.

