## **8.2 Baseline Evaluations**

Baseline evaluations are to be conducted within 7 days prior to starting treatment, unless otherwise specified below. In the event that the participant's condition is deteriorating, laboratory evaluations should be repeated within 48 hours prior to initiation of the first cycle of therapy.

- 8.2.1 Enrollment into Advantage eClinical Treatment Segment once all eligibility criteria are confirmed.
- 8.2.2 Interim medical history, including HIV-related and AIDS-defining events.
- 8.2.3 Review of concurrent medications as defined in [Section 8.1.3](#).
- 8.2.4 Complete physical examination including vital signs, weight, assessment of signs and symptoms, neuropathy evaluation (i.e., pain, aching, or burning in hands or feet), and performance status.
- 8.2.5 Tumor assessments with photographic record must be performed prior to initiating treatment. These may be performed on Day 1, but no earlier than 7 days before initiating study treatment. If the screening tumor assessments with photographic record are performed within 7 days before initiating study treatment, the screening tumor assessments can be used as a baseline assessment. Tumor assessments and photographs should be performed as outlined in the KS Tumor Assessment MOP.
- 8.2.6 Staging criteria: KS staging will be based on the modified AIDS Clinical Trials Group (ACTG) Oncology Committee Staging Criteria as outlined in [Appendix XIII](#).
- 8.2.7 HIV plasma quantitative RNA viral load via HIV quantitative PCR within 28 days before initiating study treatment. If the HIV viral load used to determine eligibility is performed within 28 days of the start of protocol therapy, the screening viral load can be used as a baseline test. The results of the baseline HIV viral load do not need to be available prior to the start of protocol therapy.  
A CD4 T cell count is required within 28 days prior to study treatment.
- 8.2.8 Pregnancy prevention counseling for all participants before starting each new cycle of pomalidomide, as required at [Appendix VII](#). Pregnancy testing if FCBP by b-HCG with a sensitivity of at least 25 mIU/mL within 24 hours of starting pomalidomide.
- 8.2.9 Whole blood collection for serum cytokine studies (one 7 mL red top tube) ([Appendix XII](#)) on day 1 prior to the first dose.

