## **8.3 Evaluations During Treatment**

Except as noted, evaluations required to ensure safe and timely treatment may be conducted within three days prior to beginning cycles 2-12 of pomalidomide.

- 8.3.1 KS Tumor Assessment will be performed prior to every cycle.
  - 8.3.2.1 For participants with known pulmonary KS at study entry, a CXR (and CT scan, if available and clinically indicated) will be repeated every third cycle.
  - 8.3.2.2 If during the pre-treatment assessment at cycle 7 day 1 the participant has

stable disease (SD) or progressive disease (PD) the participant must discontinue treatment. If the participant has a partial response (PR) or a complete response (CR), the participant may continue with treatment for up to 12 cycles.

- 8.3.2 Photographic documentation will be completed at each visit when the KS response category changes (see KS Tumor Assessment MOP for lesion photography guidelines).
- 8.3.3 Complete physical examination including vital signs, weight, assessment of signs and symptoms and toxicity, neuropathy evaluation (i.e., pain, aching, or burning in hands or feet), and performance status.
- 8.3.4 Interim medical history, including HIV-related and AIDS-defining events.
- 8.3.5 Assessment of adherence to ART (by participant report of missed doses).
- 8.3.6 Assessment of adherence to study therapy.
- 8.3.7 Review of concurrent medications.
- 8.3.8 CBC with differential and platelets.
- 8.3.9 Serum chemistries: sodium, potassium, chloride, bicarbonate, phosphate, glucose, creatinine, albumin, AST, ALT, alkaline phosphatase, and total bilirubin.
- 8.3.10 HIV plasma quantitative RNA viral load via HIV quantitative PCR, and CD4 T cell count prior to cycles 2, 4, 7, and 10.
- 8.3.11 Pregnancy prevention counseling for all participants before starting each new cycle of pomalidomide, as required at [Appendix VII](#). Pregnancy testing if FCBP by beta-HCG with a sensitivity of at least 25 mIU/mL within 24 hours of starting each cycle of pomalidomide. Weekly pregnancy testing for FCBP is required during the first cycle. If menstrual cycles are irregular, the pregnancy testing must occur weekly for the first 28 days and then every 10-14 days while on study.
- 8.3.12 Whole blood collection for serum cytokine studies (one 7 mL red top tube) prior to treatment for cycle 3 day 1 and cycle 7 day 1 ([Appendix XII](#)).

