#### Secondary endpoints

- Changes in CD4 counts
- Changes in HIV viral loads

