#### 10.1.2 Statistical power calculation

To test the null hypothesis that the ORR = 0.10 against the alternative that it is 0.30 with pomalidomide monotherapy at the one-sided 0.10 significance level with power of 0.90 will require 30 participants. The following stopping rule is based on stopping when the probability of observing more than x dose-limiting toxicities (DLTs) in the first cycle, as defined in [Section 4.2](#), is less than 0.05 with an underlying first cycle DLT rate of 0.10.

Since the enrollment is planned to close at the end of 2023, the target number of enrollment (30 participants) may not be achieved. It is expected that 26 participants will be able to be enrolled before study enrollment closes. As an illustration of statistical power based on the assumption that the null hypothesis that the ORR = 10% against the alternative that it is 30% with pomalidomide monotherapy at the one-sided 10% significance level, statistical power of 87.5% can be achieved with 26 participants. The following stopping rule is based on stopping when the probability of observing more than x DLTs in the first cycle, as defined in [Section 4.2](#), is less than 5% with an underlying first cycle DLT rate of 10%.

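### Participants must enter with suppressed HIV, but the only planned viral-load analysis is a GEE of changes, with no count of participants who lose suppression

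*Combined protocol and SAP*

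**What the plan says.** Section 3.1.8 requires at least 12 weeks of ART and a viral load at or below 400 "copies/mL within the preceding 12 weeks prior to enrollment". Section 8.2.7 adds a baseline viral load within 28 days before treatment, with the proviso that "The results of the baseline HIV viral load do not need to be available prior to the start of protocol therapy". On treatment, Section 8.3.10 schedules "HIV plasma quantitative RNA viral load via HIV quantitative PCR, and CD4 T cell count prior to cycles 2, 4, 7, and 10"; Section 8.4.1.9 adds both tests within a week of the last dose.

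Hypothesis 1.1.3 reads: "Pomalidomide will not adversely affect CD4 counts and HIV control in HIV-positive individuals with Kaposi sarcoma in sub-Saharan Africa". The matching secondary endpoint in Section 10.1 is "Changes in HIV viral loads", and its whole analysis in Section 10.1.4 is: "Changes in CD4 counts and HIV viral load will be evaluated using generalized estimating equations". For viral load the plan gives no scale, link, contrast, test level, sidedness, margin, or rule for values below the assay limit. It does not define virologic rebound or count participants who have one.

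**The concern.** In a group selected for suppression there is little room to improve. The adverse outcome is that some participants go above 400 copies/mL while most do not move. An average over such data has many changes near zero and a few large ones. The large ones raise the standard error in step with the mean, so the statistic responds to how many participants rebound and hardly to how far.

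This matters because 1.1.3 claims absence of harm, and this analysis is the only one planned that bears on viral control. If the average shift turned out non-significant and were read as support for 1.1.3, the conclusion would rest on the low sensitivity of the analysis. A small-sample variance correction for the GEE would not remove the problem, which lies in the quantity being summarised.

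**Working it through.** **Inputs.** n = 26 (Section 3.3.1: "This study will enroll 26 participants"). The plan gives no power or detectable change for viral load, so there is no figure of its own to reproduce. The only efficacy test level, "at the one-sided 10% significance level", belongs to the overall response rate (Section 10.1.2). Three levels are therefore shown, all of them assumptions for this endpoint.

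**Equal rebounds.** Let k participants rise by d and n-k stay unchanged.
- Mean change = kd/n.
- Variance s² = d²·k(n-k)/(n(n-1)).
- t = mean/(s/√n) = sqrt(k(n-1)/(n-k)); d cancels.
- With the GEE robust standard error, z = sqrt(kn/(n-k)); d cancels again.

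| k of 26 | t | one-sided p (t) | two-sided p (t) | z (GEE) |
|---|---|---|---|---|
| 1 | 1.00 | 0.163 | 0.327 | 1.02 |
| 2 | 1.44 | 0.081 | 0.161 | 1.47 |
| 3 | 1.81 | 0.042 | 0.083 | 1.84 |
| 4 | 2.13 | 0.022 | 0.043 | 2.17 |

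Critical t values on 25 df are 1.316 (one-sided 10%), 1.708 (one-sided 5%) and 2.060 (two-sided 5%). The smallest k that reaches significance is therefore 2, 3 and 4 respectively. GEE models fitted to baseline plus four visits, with an independence working correlation and jumps of 1, 2 and 4 log10, gave the same z for each k whatever the jump.

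**Unequal rebounds.** Take four participants rising from an assumed 50 copies/mL to 1,000, 10,000, 50,000 and 100,000, with 22 unchanged.
- On log10 the changes are 1.301, 2.301, 3.000 and 3.301. The mean is 9.903/26 = 0.381 and the SD 0.962, so t = 0.381/(0.962/√26) = 2.02, just short of 2.060.
- On the copies scale the mean is 6,185 and the SD 21,532, so t = 1.46.

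**Unequal rebounds with assay noise (simulated).** With rebounds of 1 to 4 log10 and measurement SD of 0.1 to 0.3 log10 (both assumed), the chance of significance is:
- two-sided 5%: 12-22% for k = 3, 43-67% for k = 4, 70-98% for k = 5;
- one-sided 5%: 46-70% for k = 3;
- one-sided 10%: 46-70% for k = 2.

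**Staggered rebounds.** With equal rebounds starting at different visits, z = 1.955 for k = 4 and 2.257 for k = 5, so two-sided 5% needs 5. In the same runs k = 3 (z = 1.769) and k = 2 (z = 1.456) still pass the one-sided 5% and 10% limits of 1.645 and 1.282.

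**What a proportion would say.** One-sided 95% exact upper bounds:
- 0/26: 1 - 0.05^(1/26) = 10.9%
- 1/26: 17.0%
- 2/26: 22.3%
- 3/26: 27.2%

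**The case against.** **The count depends on the level chosen.** A reader might infer that the plan cannot detect fewer than four rebounds. The documents do not support a fixed threshold: four needs a two-sided 5% level that is stated nowhere. Worsening control is a one-directional question, and at one-sided 10% two equal rebounds suffice. This objection stands, which is why the result is given as a range.

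**Non-significant is not the same as no change.** A reader might also infer that two or three failures would be reported as no change. Section 10.1.4 says only that changes will be evaluated; it sets no test or decision rule for 1.1.3. A GEE also yields an estimate and interval, and several multi-log rebounds would give a positive mean shift. This stands too. What remains is that the plan names no result that would support or contradict 1.1.3.

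**Average change is an inference.** A logit-link GEE on suppressed versus not suppressed would fit the sentence. The average is still the natural reading: the endpoint is worded as changes, viral load is paired with CD4 count, and the same section names logistic regression separately for a binary outcome. If a binary model was meant, the plan needs to say so.

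**400 is not a floor.** It is an eligibility ceiling, not an assay limit, and the baseline sample may exceed it because treatment can start before the result is known. This is correct, and the denominator proposed below allows for it.

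**The proportion is also weak at n = 26.** Tested at one-sided 5% against an assumed background rebound rate of 3%, 5% or 10%, it would need 3, 4 or 6 rebounds (p = 0.042, 0.039, 0.040). Much of the insensitivity comes from the size and single-arm design, and no summary cures that. The advantage of the proportion is that it states directly how high a rebound rate the data leave open.

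**Rebounds would be visible in the data.** Individual viral loads and ART adherence are collected. The gap is that no planned analysis reports them.

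**Conclusion.** The point holds as a mismatch between the question and the planned summary. With a suppressed group at entry, a GEE of average change responds to the number of rebounds and, when they are equal, not at all to their size. In the idealised case (equal rebounds, all others unchanged, n = 26) significance needs 4, 3 or 2 rebounds at two-sided 5%, one-sided 5% or one-sided 10%. Unequal rebounds can push the number higher at each of these levels; the staggered pattern examined did so only at two-sided 5%. All of this assumes a continuous average-change model, which the plan implies but does not state.

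Whatever the level, a non-significant average without a margin cannot support hypothesis 1.1.3, and no participant-level measure of lost suppression is planned. This is a secondary endpoint and leaves the response-rate decision untouched, so the change is advisable rather than critical.

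**What to change.** In Sections 10.1 and 10.1.4:

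1. Add, as the main summary of HIV control, the proportion of participants with any post-baseline viral load above 400 copies/mL, among those at or below 400 on the Section 8.2.7 baseline test. Use all scheduled values: before cycles 2, 4, 7 and 10, and at treatment discontinuation. Stopping at cycle 7 would drop data already collected.
2. Report it with an exact one-sided upper confidence bound at a stated level.
3. List each rebound with its size, whether a later value confirms it, and the ART changes and adherence recorded under Sections 8.3.5, 8.3.7 and 8.4.1. Give each participant's last viral-load visit, since treatment lasts up to 6 cycles with stable disease and up to 12 with response.
4. Keep the GEE, on log10 viral load, as a supportive descriptive analysis, and state the rule for values below quantification.

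**Cost.** No new samples or visits are needed, and exact binomial intervals are already the plan's method for its other proportions. The statistical section is part of the protocol, so the wording needs an amendment under Section 12.3. Adding a summary is a smaller step than replacing the endpoint, which matters because version 10.0 is dated 04DEC2023, after the donor's 1 December 2023 limit for the last treatment start.

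**Downsides.** Dichotomising loses rebound size, which the listing keeps. A single value above 400 may be transient, which the listing shows. Without a control arm, the proportion bounds the rebound rate but does not attribute it to pomalidomide.

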## **11.0 ROLE OF DATA MANAGEMENT**

### **11.1 CRF Instructions**

Access to the internet data entry system for this study, Advantage eClinical, and instructions for recording of study data on CRFs will be provided by the AMC ODMC at [www.AIDSCancer.org](http://www.AIDSCancer.org). Participating institutions are responsible for submitting data and/or data forms via Advantage eClinical in accordance with the AMC Data Entry Guide and specific form instructions, within the timelines specified by the AMC's Standards of Procedure for Site Performance Measures.

### **11.2 Data Quality**

It is the responsibility of the AMC ODMC to assure the quality of data for the study (See [Appendix III](#), AMC Data and Safety Monitoring Plan). This role extends from protocol development to generation of the final study database.

### **11.3 Data Monitoring**

This study will be monitored in compliance with AMC policies and by the Clinical Data Update System (CDUS) Version 3.0. Cumulative protocol- and participant-specific CDUS data will be submitted electronically to CTEP on a quarterly basis. Reports are due January 31, April 30, July 31, and October 31. Instructions for submitting data using the CDUS can be found on the CTEP Web site (<http://ctep.cancer.gov/reporting/cdus.html>).

The AMC ODMC is responsible for compiling and submitting CDUS data to CTEP for all participants and for providing the data to the Principal Investigator for review.

## **12.0 ETHICAL AND REGULATORY CONSIDERATIONS**

### **12.1 IRB Approval and Informed Consent**

The principles of Institutional Review Board (IRB) approval and informed consent described in the Department of Health and Human Services (DHHS) regulations for the Protection of Human Subjects regulations (45 CFR Part 46) must be followed. The AMC will ensure that all participating centers, as required by the applicable regulatory requirements in each country in which the trial will be conducted, will submit any required applications to the appropriate authorities for review, acceptance, and/or permission to begin the trial. Any notification/submission should be dated and contain sufficient information to identify the protocol (ICH E6). Documentation of this authorization will be collected by the AMC before each center will be activated to enroll participants.

The sponsor's designee (AMC ODMC) must receive a copy of the letter of approval from the IRB or institutional ethics committee (IEC), which specifically approves the protocol and informed consent, before participant enrollment. The IRB/IEC must also approve any significant changes to the protocol and documentation of this approval must be sent to the AMC ODMC. The IRB/IEC must review the research project at least once every 365 days during the duration of the project. Continuing approval of the project must also be given in writing and provided to the AMC ODMC.

Records of all study review and approval documents must be kept on file by the Investigator and are participant to inspection during or after completion of the study. AEs must be reported to the IRB/IEC according to local procedures. The IRB/IEC should receive notification of completion of the study and final report within 3 months of study completion and termination. The Investigator will maintain an accurate and complete record of all submissions made to the IRB/IEC, including a list of all reports and documents submitted.

Written informed consent will be obtained from the participant. The nature, significance and risks associated with the study must be explained to the participant. The informed consent will describe the purpose of the study, the procedures to be followed, the risks and benefits of participation, all risks of the investigational agent(s) and/or study participation as listed in the model informed consent form, and all other elements of informed consent as required by regulation. A copy of the consent form will be given to the participant to keep.

In addition, any institution(s) conducting research according to the guidelines of this protocol is required to adhere to local and national laws and regulations governing the confidentiality and disclosure of health information.

### **12.2 Pomalidomide Counseling Program**

Each site must have two counselors trained by Celgene through the Counseling Program. The program is available on the internet for each person who has completed the site counselor identification form and registered with Celgene prior to completing the program. See [Appendix XI](#) for the site counselor identification form. Each participant must be counseled prior to dispensing pomalidomide and documentation is kept in the participant's records. Both the training certificates and the completed Pomalidomide Education and Counseling Guidance Documents are auditable documents and must be produced upon

request. Counselors who wish to counsel participants for different protocols at the same site or for the same protocol at different sites should indicate this on the site counselor identification form.

Each site must have two trained counselors available for counseling all participants receiving pomalidomide supplied by Celgene. Trained counselors must complete training using the online program provided free by Celgene, the pomalidomide counseling program. Registration for the program is done by completing the form found in [Appendix XI](#) and following the directions provided in the email notification. After the training is complete, the counselors must generate a training certificate and provide it to the AMC for documentation. Sites may not order pomalidomide until documentation for two trained counselors is provided to the appropriate office.

